11.2 Definitions

11.2.1 Evaluable For Adverse Events

Any patient who receives at least one dose of the study drug(s) or who experiences a dose-limiting toxicity is considered evaluable for Adverse Events. In addition, for the dose-escalation portion during Cycle 1, patients must receive at least 80% of the prescribed dose per protocol guidelines and must have the appropriate toxicity monitoring studies performed to be considered evaluable for dose limiting toxicity. Patients who do not have DLT and are not considered evaluable for toxicity will be replaced.

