5.5.1 Non-hematological dose-limiting toxicity

5.5.1.1 Any Grade 3 or greater non-hematological toxicity at least possibly attributable to protocol therapy with the specific exclusion of:

- Alopecia
- Grade 3 fatigue, anorexia, nausea, vomiting, and diarrhea not requiring hospitalization, tube-feeding, or use of TPN.
- Grade 3 liver enzyme elevation, including ALT/AST, occurring after flotetuzumab administration that returns to Grade ≤ 1 or baseline within 7 days from the start of therapy. Note: For the purposes of this study the ULN for ALT is defined as 45 U/L.
- Grade 3 or 4 fever, febrile neutropenia, or infection
- Grade 3 or 4 isolated electrolyte abnormalities that resolve with or without intervention to \leq Grade 2 within 72 hours. Electrolyte supplementation is encouraged.
- Grade 3 or 4 tumor lysis syndrome that resolves within 7 days without end-organ damage.
- Grade 3 rash that resolves (with or without supportive care) to \leq

THIS PROTOCOL IS FOR RESEARCH PURPOSES ONLY, SEE PAGE 1 FOR USAGE POLICY

Grade 2 within 7 days

- Grade 3 mucositis that resolves (with or without supportive care) to \leq Grade 2 within 7 days
- Early intervention with TPN or enteral tube feeding for anorexia, nausea not attributable to protocol therapy, or concern for poor nutritional status clearly and incontrovertibly not attributable to protocol therapy will not be considered a DLT
- Grade 3 or greater pain due to leukemia, mucositis, typhlitis, infection, or obvious injury
- Grade 3 IRR (including CRS) resolving to \leq Grade 2 within 72 hours. CRS will be defined by ASBMT consensus grading³⁶
- Cases of Hy's law ($> 3x$ ULN of ALT/AST along with $> 2x$ ULN in total bilirubin without evidence of cholestasis) will be considered a DLT if no other reason can be found to explain the observed injury (e.g. leukemia, infection, another drug, etc.).

5.5.1.2 Non-hematological toxicity that causes a delay of ≥ 14 days between treatment cycles.

5.5.1.3 Note: Allergic reactions that necessitate discontinuation of study drug will not be considered a dose-limiting toxicity.

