6.3.1 CRS Management

The following are treatment guidelines (which may be modified as needed by the responsible investigator according to the best practices of medicine) for CRS related to flotetuzumab. Early intervention at the first signs of CRS, including pyrexia, tachycardia, tachypnea and/or hypotension in the absence of alternative etiologies and in consistent temporal relationship to administration of flotetuzumab, should be undertaken.

CRS is a commonly observed event during treatment with flotetuzumab based on experience in the adult population, with the majority of patients experiencing at least 1 event of Grade 1 or 2. Based on current understanding gained from patients treated with blinatumomab and CAR T cells, CRS is likely to be a common toxicity that can be managed through supportive care and anti-cytokine interventions to allow for full activity of T cells during therapy. A consensus grading system for CRS has been proposed by the American Society for Blood and Marrow Transplantation which will be utilized for this study ([Table 1](#)).

Table 1: ASBMT CRS Consensus Grading

CRS Parameter	Grade 1	Grade 2	Grade 3	Grade 4
Fever*	Temperature \geq 38°C	Temperature \geq 38°C	Temperature \geq 38°C	Temperature \geq 38°C
		With		
Hypotension	None	Not requiring vasopressors	Requiring a vasopressor with or without vasopressin	Requiring multiple vasopressors (excluding vasopressin)
		And/or [#]		
Hypoxia	None	Requiring low-flow nasal cannula ^{#@} or blow-by supplemental oxygen	Requiring high-flow nasal cannula ^{#@} , facemask, non-rebreather mask, or Venturi mask supplemental oxygen	Requiring positive pressure (e.g., CPAP, BiPAP, intubation and mechanical ventilation)

Organ toxicities associated with CRS may be graded according to CTCAE v5.0 but they do not influence CRS grading.

*Fever is defined as temperature \geq 38°C not attributable to any other cause. In patients who have CRS then receive antipyretic or anticytokine therapy such as tocilizumab or steroids, fever is no longer required to grade subsequent CRS severity. In this case, CRS grading is driven by hypotension and/or hypoxia.

[#]CRS grade is determined by the more severe event: hypotension or hypoxia not attributable to any other cause. For example, a patient with temperature of 39.5°C, hypotension requiring 1 vasopressor, and hypoxia requiring low-flow nasal cannula is classified as grade 3 CRS.

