- Grade 3 CRS that is refractory to tocilizumab should be treated with corticosteroids. Dexamethasone is the corticosteroid of choice administered at a total daily dose of at least 0.2 – 0.4 mg/kg/day (maximum 24 mg per day) administered preferably intravenously divided 3 – 4 times daily for at least 1 day but no more than 4 days. The dose should be stopped or tapered as clinically indicated.
- If infusion reaction improves to \leq grade 2 within 72 hours, infusion may be resumed at no greater than 50% of the original rate once symptoms decrease to Grade 1. The rate may then be escalated to the original rate after 30 minutes, as tolerated. A more gradual increase in the rate of infusion may be undertaken after consultation with the study chair;
- If infusion reaction DOES NOT improve to \leq grade 2 within 72 hours or if there are multiple grade 3 infusion reactions, flotetuzumab treatment must be permanently discontinued:
 - Report as an immediately reportable event (IRE) immediately;
 - Report the event as a serious adverse event (SAE) if appropriate.

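### A child permanently stopped in Cycle 1 for repeated Grade 3 IRR/CRS, each episode settling within 72 hours, has no DLT and so never counts against the dose

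*Combined protocol and SAP*

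**What the plan says.** Four rules meet here.

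- **DLT definition (5.5.1.1).** Attributable non-hematological toxicity of Grade 3 or higher is a DLT unless listed as excluded. The list includes "Grade 3 IRR (including CRS) resolving to" Grade 2 or lower within 72 hours. It does not limit the number of episodes.
- **Stopping (6.3.1.3, 10.1(e)).** After a Grade 3 reaction that improves in time, "infusion may be resumed at no greater than 50% of the original rate once symptoms decrease to Grade 1". If it does not improve within 72 hours, or "if there are multiple grade 3 infusion reactions, flotetuzumab treatment must be permanently discontinued". Separately, 10.1(e) removes a patient who has more than two discontinuations in a cycle because of adverse events.
- **Evaluability (11.2.1).** To be evaluable for DLT in Cycle 1, "patients must receive at least 80% of the prescribed dose per protocol guidelines".
- **Replacement (11.2.1, 11.3).** "Patients who do not have DLT and are not considered evaluable for toxicity will be replaced". Section 11.3 repeats this, provided the escalation or de-escalation rule has not already been met. Its decision table recognises only patients with DLT, without DLT, or with data pending.

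The CRS management text is a guideline, "which may be modified as needed by the responsible investigator according to the best practices of medicine".

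**The concern.** Section 6.3.1.3 orders the same permanent stop for two reasons. One, failure to improve within 72 hours, is a DLT. The other, repeated Grade 3 reactions that each improve in time, is not. No other DLT criterion picks it up: 5.5.1.2 concerns a delay of 14 days or more between cycles, and a stopped child has no next cycle. Many toxicities that do count allow the child to continue at a lower dose (6.2.1), so the uncounted event can have the harsher consequence.

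Safety, tolerability and the MTD/RP2D are the primary aims, and a dose level is decided by whether there are fewer than two DLTs among at most six children. A drug-related stop that the protocol itself directs, in a child who could not be kept on that dose, belongs in that count.

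**Working it through.** **1. The plan's own numbers.** Three levels of six plus a PK expansion of six is 24, and 24/0.90 = 26.7, giving 27. With 12 per level, (36 + 6)/0.90 = 46.7, giving 47. Both match Section 11.1, so the sample size is not at issue.

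**2. When is 80% of the dose reached?** Sum the daily Cycle 1 doses in Section 5.1 and Appendix IV (ng/kg):

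| Level | Total | By end of Day 8 | Day 14 | Day 21 | Day 23 | Day 24 |
|---|---|---|---|---|---|---|
| DL-1 | 7,050 | 14.9% | 40.4% | 70.2% | 78.7% | 83.0% |
| DL1 | 12,090 | 17.3% | 42.1% | 71.1% | 79.3% | 83.5% |
| DL2 | 16,830 | 16.8% | 41.8% | 70.9% | 79.2% | 83.4% |

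An uninterrupted infusion crosses 80% on Day 24 at every level. A hold at target dose that is not made up moves this later: Day 25 after 24 hours, Day 27 after 72 hours. A stop before then means replacement; a later stop means the child counts as without DLT.

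**3. What this could do to the decision.** Let d be the rate of DLTs as now defined, and q the rate of uncounted stops among children with no other DLT. The documents give neither.

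- Replaced: DLT rate among evaluable children p = d/(1 − q).
- Counted as DLT: p = d + q.
- Accept the dose with at most one DLT in six: (1 − p)^6 + 6p(1 − p)^5.

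Assume d = 20%. The q values are arbitrary: one eighth and one quarter of the adult Grade 3 or higher IRR/CRS rate at 500 ng/kg/day (4/31 = 12.9%, exact 95% CI 3.6% to 29.8%; Section 2.3.1), and a round 5%.

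| q | p replaced | p counted | Accept, replaced | Accept, counted | At least one such stop in six, 1 − (1 − q)^6 |
|---|---|---|---|---|---|
| 0 | 0.200 | 0.200 | 0.66 | 0.66 | 0% |
| 1.6% | 0.203 | 0.216 | 0.65 | 0.62 | 9% |
| 3.2% | 0.207 | 0.232 | 0.64 | 0.58 | 18% |
| 5% | 0.211 | 0.250 | 0.63 | 0.53 | 26% |

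**4. Sensitivity.** Letting the level stop early at 0/3, otherwise 1/3 then 0/3, acceptance is (1 − p)^3 + 3p(1 − p)^5: 0.70 versus 0.67, 0.69 versus 0.64, and 0.69 versus 0.60 for the three non-zero rates. At q = 3.2% with six patients, d = 10% gives 0.88 versus 0.82, and d = 30% gives 0.40 versus 0.35. The possible expansion to 12 patients (11.2.2) is not modelled.

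**The case against.** The strongest reply is that the size is unsupported. The documents report no child or adult stopped for repeated short Grade 3 reactions. Step-up dosing and dexamethasone prophylaxis, both used here, are said in Section 2.3.1 to have lowered the incidence of IRR/CRS. The adult median duration of 2.5 days for Grade 3 or higher events shows that short events occur, not that they recur after restart. All of this stands: the table illustrates and does not estimate.

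A reader might also take the three DLTs among nine adults at 700 ng/kg/day as evidence that such stops will be common at DL2. Section 2.3.1 does not support that: one of the three was labelled CRS, the others were syncope and arthralgia/myalgia, and neither duration nor recurrence is given.

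The stops would be seen. Section 6.3.1.3 requires immediate reporting, the study chair's DLT calls are reviewed weekly (14.3.2), and the events appear in the descriptive toxicity summary. That is true, but no written rule carries them into the dose decision.

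The 80% requirement might mean the dose as modified under Section 6. The stopped child would then count as having tolerated the dose, which is worse than replacement.

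Finally, the omission could be deliberate, since 5.5.1.3 says "Allergic reactions that necessitate discontinuation of study drug will not be considered a dose-limiting toxicity". That note covers allergic reactions only; nothing comparable is written for repeated IRR/CRS.

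**Conclusion.** The gap is real on the text and should be closed. When the stop is followed, a child permanently taken off drug in Cycle 1 for repeated, individually brief, attributable Grade 3 IRR/CRS does not count against the dose. The same holds for removal under 10.1(e) because of such reactions, which matters mainly where a site has departed from the 6.3.1.3 stop and restarted.

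A reader might infer that severe CRS in general escapes the DLT count. It does not. Attributable Grade 4 or 5 IRR/CRS counts, and so does Grade 3 IRR/CRS that has not improved within 72 hours. On organ effects the grading table says "Organ toxicities associated with CRS may be graded according to CTCAE v5.0 but they do not influence CRS grading", so an attributable organ toxicity of Grade 3 or higher that is not on the exclusion list can be a DLT in its own right. Nor can one infer that the MTD/RP2D is biased by a known amount. The differences of about 3, 6 and 10 percentage points rest on assumed values of d and q, and vanish if q is zero.

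One ambiguity remains. The protocol does not say whether a return to Grade 3 soon after restart is a new reaction or a failure to resolve within 72 hours, and the DLT call depends on the answer.

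**What to change.** Add to Section 5.5.1:

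*Attributable IRR/CRS that leads to permanent discontinuation of flotetuzumab in Cycle 1, because of two or more Grade 3 reactions (Section 6.3.1.3) or under Section 10.1(e), is a DLT regardless of the time to resolution of each episode; such patients are not replaced.*

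Keep the exclusion of a single Grade 3 reaction resolving within 72 hours, and the allergic-reaction exclusion. The sentence gives the undefined term multiple a number and, for stopped children, makes the new-reaction or non-resolution question irrelevant.

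It needs no extra patients or visits, but has three costs:

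- **More caution.** A dose is somewhat more likely to be declared above the MTD, and failure at DL-1 closes the study (5.3.1). The expansion to 12 in 11.2.2 eases this only if its conditions are met: readily reversible effects, one DLT not dose-related, and agreement of all named parties.
- **Dependence on the stop.** Investigators may modify the 6.3.1.3 guideline, so two children with the same reactions could be classified differently. Including 10.1(e) narrows this but does not remove it.
- **Episode counts.** Routine adverse event forms record only the worst grade per cycle (13.4.1). The count must come from the immediate report under 6.3.1.3 or the DLT report to the study chair (5.4).

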11.2.2 Maximum Tolerated Dose

- The MTD will be the maximum dose at which fewer than one-third of patients experience DLT (See [Section 5.5](#) during Cycle 1 of therapy).
- If two or more of a cohort of up to six patients experience DLT at a given dose level, then the MTD has been exceeded and dose escalation will be stopped. If review of the DLTs suggests that they would potentially be acceptable (e.g., because of rapid reversibility, different classes of Adverse Effects) or are potentially attributable to disease rather than therapy, then expansion of the cohort to 12 patients to better assess tolerability of this dose level will be considered assuming the following conditions are met:
 - One of the DLTs does not appear to be dose-related
 - The Adverse Effects are readily reversible

THIS PROTOCOL IS FOR RESEARCH PURPOSES ONLY, SEE PAGE 1 FOR USAGE POLICY

- The study chair, DVL statistician, DVL committee chair or vice chair, IND sponsor, and CTEP all agree that expansion of the cohort is acceptable

If fewer than 1/3 of patients in the expanded cohort experience dose-limiting toxicities, the dose escalation can proceed.

- The DLTs observed in the pharmacokinetic (PK) expansion cohort will be counted towards the total number of DLTs observed at the MTD during the dose escalation portion of the study. If $\geq 1/3$ of the cohort of patients at the MTD (during the dose escalation plus the PK expansion) experience DLT then the MTD will be exceeded.

11.3 Dose Escalation and Determination of MTD

The rolling six phase 1 trial design will be used for the conduct of this study.³⁵ Two to six patients can be concurrently enrolled onto a dose level, dependent upon (1) the number of patients enrolled at the current dose level, (2) the number of patients who have experienced DLT at the current dose level, and (3) the number of patients entered but with tolerability data pending at the current dose level. However, enrollment will be staggered so that no more than 1 patient initiates enrollment every 7 days for dose levels greater than DL1. Accrual is suspended when a cohort of six has enrolled or when the study endpoints have been met.

Dose level assignment is based on the number of participants currently enrolled in the cohort, the number of DLTs observed, and the number of participants at risk for developing a DLT (i.e., participants enrolled but who are not yet assessable for toxicity). For example, when three participants are enrolled onto a dose cohort, if toxicity data is available for all three when the fourth participant entered and there are no DLTs, the dose is escalated and the fourth participant is enrolled to the subsequent dose level. If data is not yet available for one or more of the first three participants and no DLT has been observed, or if one DLT has been observed, the new participant is entered at the same dose level. Lastly, if two or more DLTs have been observed, the dose level is de-escalated. This process is repeated for participants five and six. In place of suspending accrual after every three participants, accrual is only suspended when a cohort of six is filled. When participants are inevaluable for toxicity, they are replaced with the next available participant if escalation or de-escalation rules have not been fulfilled at the time the next available participant is enrolled onto the study.

The following table provides the decision rules for enrolling a patient at (i) the current dose level (ii) at an escalated dose level, (iii) at a de-escalated dose level, or whether the study is suspended to accrual:

# Pts Enrolled	# Pts with DLT	# Pts without DLT	# Pts with Data Pending	Decision
2	0 or 1	0, 1 or 2	0, 1 or 2	Same dose level

THIS PROTOCOL IS FOR RESEARCH PURPOSES ONLY, SEE PAGE 1 FOR USAGE POLICY

2	2	0	0	De-escalate*
3	0	0, 1 or 2	1, 2 or 3	Same dose level
3	1	0, 1 or 2	0, 1 or 2	Same dose level
3	0	3	0	Escalate**
3	≥ 2	0 or 1	0 or 1	De-escalate*
4	0	0, 1, 2 or 3	1, 2, 3 or 4	Same dose level
4	1	0, 1, 2 or 3	0, 1, 2 or 3	Same dose level
4	0	4	0	Escalate**
4	≥ 2	0, 1 or 2	0, 1 or 2	De-escalate*
5	0	0, 1, 2, 3 or 4	1, 2, 3, 4 or 5	Same dose level
5	1	0, 1, 2, 3 or 4	0, 1, 2, 3 or 4	Same dose level
5	0	5	0	Escalate**
5	≥ 2	0, 1, 2 or 3	0, 1, 2 or 3	De-escalate*
6	0	0, 1, 2, 3, or 4	2, 3, 4, 5 or 6	Suspend
6	1	0, 1, 2, 3 or 4	0, 1, 2, 3 or 4	Suspend
6	0 or 1	5 or 6	0 or 1	Escalate**
6	≥ 2	0, 1, 2, 3 or 4	0, 1, 2, 3 or 4	De-escalate*

* If six patients already entered at next lower dose level, the MTD has been defined.

** If final dose level has been reached, the recommended dose has been reached.

If two or more of a cohort of up to six patients experience DLT at a given dose level, then the MTD has been exceeded and dose escalation will be stopped (see [Section 11.2.2](#) for exception to rule).

In addition to determination of the MTD, a descriptive summary of all toxicities will be reported.

11.4 Inclusion of Children, Women and Minorities

Racial Categories	PLANNED ENROLLMENT REPORT				Total	
	Ethnic Categories					
	Not Hispanic or Latino		Hispanic or Latino			
	Female	Male	Female	Male		
American Indian/ Alaska Native	0	0	0	0	0	
Asian	0	1	0	0	1	
Native Hawaiian or Other Pacific Islander	0	0	0	0	0	
Black or African American	3	3	0	0	6	
White	14	20	3	3	40	
More Than One Race	0	0	0	0	0	
Total	17	24	3	3	47	

THIS PROTOCOL IS FOR RESEARCH PURPOSES ONLY, SEE PAGE 1 FOR USAGE POLICY

The study is open to all participants regardless of gender or ethnicity. Review of accrual to past COG studies of new agents demonstrates the accrual of both genders and all NIH-identified ethnicities to such studies. Efforts will be made to extend the accrual to a representative population, but in a Phase 1 trial which will accrue a limited number of patients, a balance must be struck between patient safety considerations and limitations on the number of individuals exposed to potentially toxic or ineffective treatments on the one hand and the need to explore gender, racial, and ethnic aspects of clinical research on the other. If differences in outcome that correlate to gender, racial, or ethnic identity are noted, accrual may be expanded or additional studies may be performed to investigate those differences more fully.

11.5 Pharmacokinetic and Correlative Studies and Response Analysis

A descriptive analysis of pharmacokinetic (PK) parameters of flotetuzumab will be performed to define systemic exposure, drug clearance, and other pharmacokinetic parameters. The PK parameters will be summarized with simple summary statistics, including means, medians, ranges, and standard deviations (if numbers and distribution permit).

While the primary aim of this study is to evaluate the toxicity of flotetuzumab, patients will have disease evaluations performed as indicated in [Section 8.1](#). Disease response will be assessed according to the revised AML International Working Group (IWG) criteria³⁷ and will be reported descriptively.

CD123 expression will be analyzed in an exploratory fashion, both using a binary scale and using a continuous scale to evaluate whether there are correlations between CD123 expression and antitumor effects. Anti-drug antibody analyses will be measured by MacroGenics. Biomarkers, including those identified in the secondary objectives, will be evaluated for association with cytogenetic/molecular features and outcome.

All these analyses will be descriptive and exploratory and hypothesis-generating in nature.

12.0 EVALUATION CRITERIA

12.1 Common Terminology Criteria for Adverse Events (CTCAE)

The descriptions and grading scales found in the revised NCI Common Terminology Criteria for Adverse Events (CTCAE) version 5.0 will be utilized for AE reporting. All appropriate treatment areas should have access to a copy of the CTCAE version 5.0. A copy of the CTCAE version 5.0 can be downloaded from the CTEP website (http://ctep.cancer.gov/protocolDevelopment/electronic_applications/ctc.htm).

12.2 Response Criteria for Patients with Leukemia

Patients must have received ≥ 1 cycle of flotetuzumab, be evaluable for DLT, and have had ≥ 1 bone marrow evaluation(s) following treatment. Response will be defined as best response after up to 4 cycles. The AML response criteria are derived from the revised AML International Working Group (IWG) Criteria.³⁸ It is anticipated that patients who achieve morphologic remission with study treatment may proceed to subsequent allogeneic HSCT at the treating physician's discretion.

THIS PROTOCOL IS FOR RESEARCH PURPOSES ONLY, SEE PAGE 1 FOR USAGE POLICY

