If a patient experiences progressive disease at any time point, they must discontinue protocol therapy. Patients with at least a partial response (PR) following Cycle 2 may continue on subsequent cycles of flotetuzumab for a total of up to 6 cycles. Patients should discontinue protocol therapy if they have not achieved at least a PR following Cycle 2. No planned step-up dosing will occur during subsequent cycles unless there is an infusion interruption of > 3 days between cycles of flotetuzumab. For patients with no evidence of disease after Cycle 1, subsequent cycles should be interrupted until ANC $\geq 500 \mu\text{L}$ and platelets $\geq 20,000/\text{mm}^3$. Patients with persistent disease are permitted to continue flotetuzumab regardless of ANC and platelet counts.

Pharmacokinetic sampling and monitoring for ADAs will be performed in all patients (see [Appendix VI-A](#), [Appendix VI-B](#), [Appendix VI-C](#), and [Appendix VII](#)). In consenting patients, correlative studies to characterize the tumor microenvironment will be obtained, which will include peripheral blood studies and bone marrow (see [Appendix X](#) and [Appendix XII](#)). Correlative plasma studies as a measurement of CRS and biomarkers of response will also be obtained in consenting patients (see [Appendix XI](#)).

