9.3 Useful Links and Contacts

- CTEP Forms, Templates, Documents:
<http://ctep.cancer.gov/forms/>
- NCI CTEP Investigator Registration:
[contact]
- CTEP Identity and Access Management (IAM) account:
<https://ctepcore.nci.nih.gov/iam/>
- CTEP Associate Registration and IAM account help:
[contact]
- IB Coordinator:
[contact]

10.0 CRITERIA FOR REMOVAL FROM PROTOCOL THERAPY AND OFF STUDY CRITERIA**10.1 Criteria for Removal from Protocol Therapy**

- a) Clinical (including physical examination or serum tumor markers) or radiographic

THIS PROTOCOL IS FOR RESEARCH PURPOSES ONLY, SEE PAGE 1 FOR USAGE POLICY

evidence of progressive disease (See [Section 12](#)).

- b) Have not achieved at least a PR following 2 successive treatment cycles.
- c) Adverse Events requiring removal from protocol therapy (See [Section 13](#)).
- d) Development of a DLT following 1 dose reduction.
- e) An infusion stop or delay of more than 2 weeks due to AE or more than 2 discontinuations per cycle due to AE (does not apply for prolongation of the scheduled treatment free period of a cycle).
- f) Refusal of protocol therapy by patient/parent/guardian
- g) Non-compliance that in the opinion of the investigator does not allow for ongoing participation.
- h) Completion of 6 cycles of therapy.
- i) Physician determines it is not in the patient's best interest.
- j) Repeated eligibility laboratory studies (CBC with differential, bilirubin, ALT (SGPT) or serum creatinine) are outside the parameters required for eligibility prior to the start of flotetuzumab (See [Section 8.1](#)).
- k) Study is terminated by Sponsor.
- l) Pregnancy

Patients who are removed from protocol therapy during Cycle 1 should continue to have the required observations in [Section 8.1](#) until the originally planned end of the cycle or until all adverse events have resolved per [Section 13.4.4](#), whichever happens LATER. The only exception is with documentation of the patient's withdrawal of consent. Patients who are removed from protocol therapy in subsequent cycles should have the necessary observations to ensure adequate clinical care.

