12.2.5 Progressive Disease (PD)

Increase in the absolute number of circulating (in peripheral blood) or bone marrow blasts of at least 50% from nadir or development of extramedullary disease.

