12.2.8 Unevaluable

Aplastic or severely hypocellular marrow with any blast percentage. In this instance, marrow evaluation should be repeated weekly until response determination can be made through at least Day 49.

12.2.9 Bone Marrow Classification:

M1 is < 5% blasts
M2 is 5-25% blasts
M3 is > 25% blasts

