- j. Bone marrow aspirate. Prior to Cycle 1 and at the end of Cycle 1.
- k. Urinalysis. Prior to Cycle 1.
- l. Pregnancy test. Prior to Cycle 1 for women of childbearing potential.
- m. ECHO or gated radionuclide study. Prior to Cycle 1.

THIS PROTOCOL IS FOR RESEARCH PURPOSES ONLY, SEE PAGE 1 FOR USAGE POLICY

- n. EKG. Prior to Cycle 1.
- o. Neurologic exam. Prior to Cycle 1.
- p. Ht/Wt/BSA. Prior to Cycle 1.
- q. NGS MRD comparison with flow cytometry MRD. In consenting patients only at the time of bone marrow evaluation. See [Section 8.5](#) for details.
- r. CD3 T-lymphocyte quantification. In consenting patients, blood samples will be collected on Cycle 1 Days 1, 8, 15, 22, and 29. See [Section 8.6](#) for details.
- s. Cytokine production measurement. In consenting patients, blood samples will be collected on Cycle 1, Day 1 (prior to flotetuzumab infusion), and on Cycle 1, Day 8. Additionally, if patients experience IRR/CRS, blood samples will be collected from consenting patients at the time of IRR/CRS and at the time of IRR/CRS resolution. See [Section 8.7](#) for details.
- t. Immunogenicity study. One sample to be collected from all patients on Cycle 1, Day 1 (pre-infusion). See [Section 8.3](#) for details.
- u. Tumor microenvironment profiling. Prior to Cycle 1. See [Section 8.8](#) for details.
- v. Clot section/biopsy. Prior to Cycle 1 and at the end of Cycle 1. To be performed in conjunction with the bone marrow aspiration.
- w. CD123 site density analysis. In consenting patients prior to Cycle 1. To be performed on the collected bone marrow aspirate. See [Section 8.4](#) for details.
- x. Cytogenetics and FISH. Prior to Cycle 1. To be performed on the collected bone marrow aspirate. It is recommended that cytogenetics/FISH be performed by a COG-approved laboratory.
- y. Flow cytometry with MRD determination. At the end of Cycle 1 with bone marrow evaluation.

This listing only includes evaluations necessary to answer the primary and secondary aims. OBTAIN OTHER STUDIES AS REQUIRED FOR GOOD CLINICAL CARE.

Comments

(Include any held doses, or dose modifications)

THIS PROTOCOL IS FOR RESEARCH PURPOSES ONLY, SEE PAGE 1 FOR USAGE POLICY

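### Section 12.2 ties response to DLT evaluability, so dose-escalation patients without DLT who progress or die before about day 23 drop out of the response rate

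*Combined protocol and SAP*

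**What the plan says.** The opening of Section 12.2 sets three joint conditions for response: at least one "cycle of flotetuzumab, be evaluable for DLT, and have had" at least one marrow evaluation after treatment. Response is then the best result over up to four cycles.

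The middle condition leads back to Section 11.2.1: "for the dose-escalation portion during Cycle 1, patients must receive at least 80% of the prescribed dose per protocol guidelines", with the appropriate toxicity monitoring done. A patient who has a DLT is not replaced. For the rest, "Patients who do not have DLT and are not considered evaluable for toxicity will be replaced".

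Section 2.5 says: "If a patient experiences progressive disease at any time point, they must discontinue protocol therapy". Section 5.2 repeats this.

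Section 11.5 says that response is reported descriptively and names no analysis set. Section 12.2.4 leaves partial response out of the calculation of response to the regimen, so a rate is intended. Unevaluable (12.2.8) is reserved for "Aplastic or severely hypocellular marrow with any blast percentage". Death appears in Section 10.2 only as an off-study criterion.

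**The concern.** The 80% rule serves the dose-finding question: a patient who had too little drug and no DLT says little about tolerability and is reasonably replaced. Section 12.2 borrows the same rule to decide who counts for activity, where it works differently. In relapsed or refractory AML, a common reason to receive little of Cycle 1 without a DLT would be that the leukemia progressed or the patient died of it. Those patients are treatment failures for activity, yet they leave both numerator and denominator.

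At stake is the response rate for secondary aim 1.2.2, the preliminary description of anti-tumor activity. If the excluded patients respond less often than the evaluable ones, the reported rate is too high. Because the rule selects on early outcome, the response set should be settled before results are known.

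**Working it through.** **Step 1: the plan's own sample size.** Section 11.1 gives up to 18 patients for the MTD/RP2D, up to 6 for PK expansion and 10% attrition: (18 + 6)/(1 − 0.10) = 26.7, rounded up to 27. This reproduces the stated anticipated maximum of 27. The documents give no expected response rate and no expected number of early failures.

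**Step 2: when 80% of the Cycle 1 dose is reached.** Inputs are the step-up schedules in Section 5.1 and Appendices IV-A to IV-C, in ng/kg, assuming 28 uninterrupted infusion days and that the prescribed dose is the planned total.

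| Level | Planned total | 80% | Time to 80% |
|---|---|---|---|
| DL1 | 30+60+100+200+300+400+22×500 = 12,090 | 9,672 | 6 + (9,672 − 1,090)/500 = 23.2 days |
| DL-1 | 30+2×60+2×100+2×200+21×300 = 7,050 | 5,640 | 7 + (5,640 − 750)/300 = 23.3 days |
| DL2 | 30+100+200+300+400+500+600+21×700 = 16,830 | 13,464 | 7 + (13,464 − 2,130)/700 = 23.2 days |

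Share of the planned dose received by a patient who stops early:

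| Stop after | DL1 | DL-1 | DL2 |
|---|---|---|---|
| Day 14 | 5,090/12,090 = 42.1% | 2,850/7,050 = 40.4% | 7,030/16,830 = 41.8% |
| Day 21 | 8,590/12,090 = 71.1% | 4,950/7,050 = 70.2% | 11,930/16,830 = 70.9% |

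A no-DLT patient who stops at either point is not evaluable for DLT and so fails Section 12.2.

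**Step 3: does anything bring these patients back?** Section 10.1 says: "Patients who are removed from protocol therapy during Cycle 1 should continue to have the required observations in" Section 8.1, and Appendix IV-A lists among those observations "Bone marrow aspirate. Prior to Cycle 1 and at the end of Cycle 1". Section 12.2.5 allows progression to be shown in blood: "Increase in the absolute number of circulating (in peripheral blood) or bone marrow blasts of at least 50% from nadir". So some early progressors will have a documented progression, and some a marrow. They still fail the DLT-evaluability condition. Stable disease (12.2.6) is a residual category, but it too applies only to patients who pass the opening conditions. No text assigns the others to non-response.

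**Step 4: effect on the rate.** With T treated, E excluded and R responders, none among the excluded, the reported rate divided by the all-treated rate is [R/(T − E)]/(R/T) = T/(T − E), whatever R is. The counts below are assumptions, not figures from the plan: T = 27, R = 5.

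| Excluded | Reported rate | Ratio to 5/27 = 18.5% |
|---|---|---|
| 1 | 5/26 = 19.2% | 27/26 = 1.04 |
| 2 | 5/25 = 20.0% | 27/25 = 1.08 |
| 3 | 5/24 = 20.8% | 27/24 = 1.125 |
| 6 | 5/21 = 23.8% | 27/21 = 1.29 |

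With 2 to 8 responders and 1 to 3 exclusions, the shift runs from 2/26 − 2/27 = 0.3 to 8/24 − 8/27 = 3.7 percentage points. The exact (Clopper-Pearson) 95% interval for 5/24 is 7.1% to 42.2%, about 35 points wide.

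**The case against.** The case for leaving the plan alone has weight. Response is secondary, described as preliminary and reported descriptively; no test, sample size, stopping rule or dose decision uses it. The illustrated shift is small against the confidence interval, and there is no bias if the excluded patients would have responded equally often. The 27 already allows for attrition, so treating it as the number treated is generous. An evaluable set is also a legitimate estimate of activity in adequately exposed patients, and the adult data in Section 2.3.1 use one: 27 response-evaluable of 31 treated at the adult RP2D. All of this stands. It limits the weight of the point and argues for keeping the evaluable-set rate, but not for showing it alone. On scale only, the adult CR/CRi rate of 5/27 = 18.5% would be 5/31 = 16.1% if none of the other four responded; the protocol does not say why they were not evaluable.

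A reader might infer more than the documents support:

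- **Everyone who stops before Day 29 is excluded.** That requires reading receipt of at least one cycle as completion. The phrase is undefined, so it needs clarifying, but it does not demonstrate an exclusion.
- **The 80% rule removes early progressors throughout the trial.** It is worded for dose escalation and does not remove patients with a DLT. In the PK expansion only the one-cycle and marrow conditions clearly apply.
- **Day 23 is a fixed cut-off.** It assumes the prescribed dose is the planned 28-day total. The infusion-rate reductions in Section 6.3.1 leave that open to interpretation.
- **The data to classify every early failure are in hand.** Section 10.1 says only that observations should continue, and Section 10.2 takes patients off study on death, withdrawal of consent or enrollment on another COG therapeutic study.
- **The inflation is large.** Big shifts need a large share of patients to be excluded, and no figure in the plan supports that.

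**Conclusion.** The point holds in limited form. In dose escalation, Section 12.2 leaves out no-DLT patients who progress or die before about day 23 of uninterrupted infusion, and the plan nowhere counts them as non-responders. Section 12.2 does not use the word denominator; that reading follows from its heading, its mandatory wording and the reference in 12.2.4 to calculating response.

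The direction is upward if excluded patients respond less often than evaluable ones. The size is unknown: a factor of 1.04 to 1.125 for 1 to 3 exclusions among 27 treated, on assumed counts and with no excluded responder. Replacing these patients for dose finding is not at fault, and the MTD and RP2D are unaffected. This is a cheap improvement, not a flaw in the primary design.

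**What to change.** In Sections 12.2 and 11.5, report best response over all eligible patients who received any flotetuzumab. Count early progression, death, or no post-treatment marrow as non-response. Give the Section 12.2 evaluable-set rate beside it, and list the number excluded by reason, so that stops unrelated to leukemia, such as withdrawal of consent, can be told apart from early failures.

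As a clarification, state whether receiving at least one cycle means starting or completing it, and how this applies to patients stopped by a DLT and to those in the PK expansion.

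The cost is wording. No extra patients or procedures are needed, because a patient without an assessment is classified by rule. The downside is a slightly lower response rate; keeping the evaluable-set figure preserves a rate of the same general type as the adult one.
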